15.1 Maximum Tolerated Dose (Primary Endpoint)

Analysis set: DLT analysis set

The maximum tolerated dose (MTD) is defined as the highest dose for a given schedule at which there is no more than 1 DLT in 6 participants. The DLT information will be based on the "Adverse Events" eCRF page where "Dose-limiting toxicity?" = Yes.

A summary table of DLTs during the first cycle of study treatment will be provided including the following information:

- Number of subjects with no DLT
- Number of subjects with one or more DLTs

A listing of DLTs will also be provided.

15.2 Adverse Events

Analysis set: SAF

Treatment emergent adverse events (TEAEs) are defined as those events with onset dates occurring within the on-treatment period as defined in Section 9.

All analyses described in Section 15.2 will be based on TEAEs if not otherwise specified.

Incomplete AE-related dates will be handled as follows:

- In case the onset date is missing completely or missing partially but the onset month and year, or the onset year are equal to the start of trial treatment then the onset date will be replaced by the minimum of start of trial treatment and AE resolution date.
- In all other cases the missing onset day or missing onset month will be replaced by 1.
- Incomplete stop dates will be replaced by the last day of the month (if day is missing only), if
 not resulting in a date later than the date of subject's death. In the later case the date of death
 will be used to impute the incomplete stop date.
- In all other cases the incomplete stop date will not be imputed. If stop date of AE is after date
 of cut-off outcome of AE is ongoing at cut-off.

AEs will be summarized and presented based on the information collected from the "Adverse Events" eCRF page. Pretreatment AEs are defined as AEs that were reported or worsened after signature of the informed consent form up to the start of the trial drug (M4344 or carboplatin, as applicable).

- Related adverse events: adverse events with relationship to study treatment reported by the investigator and those of unknown relationship (i.e. missing data for relationship).
 - M4344: "Relationship to VX-803" (Parts A and B1) or "Relationship with M4344" (Part A2) = "Related", "Possibly Related", or missing
 - Carboplatin: "Relationship to carboplatin" = "Related", "Possibly Related", or missing
- Serious adverse events (SAEs): serious adverse events (serious adverse events = "Yes").
- AEs leading to permanent treatment discontinuation
 - M4344: "VX-803 Action Taken" (Parts A and B1) or "Action(s) taken with M4344" (Part A2) = "DrugWithdrawn"

- Carboplatin: "Carboplatin Action Taken" = "Drug Withdrawn"
- AEs leading to temporary treatment discontinuation
 - M4344: "VX-803 Action Taken" (Parts A and B1) or "Action(s) taken with M4344" (Part A2) = "Drug Interrupted"
 - Carboplatin: "Carboplatin Action Taken" = "Drug Interrupted"

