The following conversion factors will be used to convert days into months or years: 1 month = 30.4375 days, 1 year = 365.25 days.

Handling of missing data:

Unless otherwise specified, missing data will not be replaced.

In all subject data listings, imputed values will be presented and flagged as such.

Missing statistics, e.g. when they cannot be calculated, should be presented as "nd" (not done). For example, if n=1, the measure of variability (StdDev) cannot be computed and will be presented as "nd".

Treatment day

Treatment day is defined relative to the start of a treatment. Treatment Day 1 is the day of the first administration of trial drug (M4344 or carboplatin as applicable to the study part). The day before Treatment Day 1 is defined as Treatment Day -1. (No Treatment Day 0 is defined.)

On-treatment period

The on-treatment period is defined as the date of the first dose of a trial drug (M4344 or carboplatin as applicable) until the minimum of the following: date of last dose of study treatment + 30 days and the date of death.

Definiton of Missing category

If not otherwise specified the following categories will be summarized under the missing category:

- missing
- unknown

SAS version:

All analyses will be performed using SAS® Software version 9.4 or higher.

Presentation of PK Concentration Data

PK concentration data will be descriptively summarized by part, treatment and day using: number of non-missing observations, Mean, StdDev, coefficient of variation (CV%), Min, Median and Max.

Descriptive statistics of PK concentration data will be calculated using values with the same precision as the source data, and rounded for reporting purposes only. The following conventions will be applied when reporting descriptive statistics of PK concentration data:

Min, Mean, Median and Max: 3 significant digits
 StdDev: 4 significant digits
 CV%: 1 decimal place

Presentation of PK Parameter Data

PK parameter data will be descriptively summarized by part, treatment and day using: number of non-missing observations, Mean, StdDev, CV%, Min, Median, Max, geometric mean (GeoMean), geometric coefficient of variation (GeoCV) and the 95% CI for the GeoMean (lower 95% CI for GeoMean, upper 95% CI for GeoMean).

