9.11.2 Incomplete Adverse Events Dates

Incomplete AE-related dates are imputed for use in determining whether the AE is considered Treatment-Emergent. Incomplete dates will be imputed as follows:

- If the AE onset date is missing completely, then the onset date will be replaced by the start of study treatment.
- If only the day part of the AE onset date is missing, but the month and year are equal to the start of study treatment, then the AE onset date will be replaced by the start of study treatment. For example, if the AE onset date is --/JAN/2015, and study treatment start date is 15/JAN/2015, then the imputed AE onset date will be 15/JAN/2015. If the end date or resolution date indicates that the AE has stopped before start of treatment, this date will be used for imputation instead of start of treatment date.

- If both the day and month of the AE onset date are missing but the onset year is equal to the start of study treatment, then the onset date will be replaced by the start of study treatment. For example, if AE onset date is --/---/2014, and study treatment start date is 19/NOV/2014, then the imputed AE onset date will be 19/NOV/2014.
- In all other cases the missing onset day or missing onset month will be replaced by 1.
- Incomplete stop date will be replaced by the last day of the month (if only the day is missing),
 if not resulting in a date later than the date of participant's death. In the latter case the date of
 death will be used to impute the incomplete stop date.

In all other cases the incomplete stop date will not be imputed. If stop date of AE is after date of cut-off this date will be kept.

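### The Parts A/A2/B1 rule for partial adverse event onset dates does not limit the year match to dates without a month, so its literal wording makes some pre-treatment and post-treatment events treatment-emergent

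*SAP*

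**What the plan says.** In the plan for Parts A, A2 and B1, Section 15.2 defines treatment-emergent adverse events (TEAEs) as "those events with onset dates occurring within the on-treatment period as defined in Section 9". Under the on-treatment period in Section 9, that period ends at the earlier of "date of last dose of study treatment + 30 days and the date of death".

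Section 15.2 handles an incomplete onset date in two steps:

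- The first step covers an onset that is wholly missing, and one that is "missing partially but the onset month and year, or the onset year are equal to the start of trial treatment". Such an onset is set to whichever comes earlier, first dose or resolution of the event.
- The second step is a fallback for whatever the first step leaves over: "In all other cases the missing onset day or missing onset month will be replaced by 1".

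The separate Part C plan treats the two kinds of partial date in separate bullets of Section 9.11.2. One begins "If only the day part of the AE onset date is missing, but the month and year are equal" and the other "If both the day and month of the AE onset date are missing but the onset year is equal to the start of study treatment". There the year is compared on its own only when no month is recorded.

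**The concern.** In the Parts A/A2/B1 sentence the two match conditions are joined by *or* and apply to every partially missing date. A date with only the day missing, whose recorded month differs from the month of first dose, still satisfies the year condition. It is therefore caught by the first step and never reaches the fallback that would keep its month and set the day to 1.

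TEAE status decides which events enter the frequency tables in Sections 15.2.1 and 15.2.2, and Section 5 lists adverse events among the primary endpoints of all three parts. An event known to have begun before treatment, or after the on-treatment period, should not enter those tables because its day was not recorded. The first kind would also conflict with the definition of pre-treatment events in Section 15.2 itself. A second risk is reproducibility: two programmers could code the sentence differently and obtain different TEAE counts.

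**Working it through.** The plan states no figure to reproduce. The check is to code the onset rule in both possible ways and compare the results.

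**Inputs from the documents.** The trigger, the replacement and the fallback are from Section 15.2. The on-treatment period is from Section 9. The comparison structure is from Section 9.11.2 of the Part C plan.

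**Assumptions for illustration, not from the documents.** First dose is 15 Jun 2018 and last dose 31 Aug 2018. The on-treatment period then ends on 31 Aug + 30 days = 30 Sep 2018. If there is no resolution date, the minimum is taken as treatment start.

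**Literal reading.** Trigger = onset wholly missing, OR month and year match, OR year matches.

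**Respective reading.** Trigger = onset wholly missing, OR (month recorded AND month and year match), OR (month not recorded AND year matches).

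In both, a triggered onset becomes min(treatment start, resolution date). Otherwise a missing day or month becomes 1.

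| Recorded onset | Resolution | Literal reading | Respective reading |
|---|---|---|---|
| --/MAR/2018 | ongoing | 15 Jun 2018, TEAE | 1 Mar 2018, not TEAE |
| --/MAR/2018 | 20 Jul 2018 | 15 Jun 2018, TEAE | 1 Mar 2018, not TEAE |
| --/MAR/2018 | 30 Apr 2018 | 30 Apr 2018, not TEAE | 1 Mar 2018, not TEAE |
| --/JUN/2018 | ongoing | 15 Jun 2018, TEAE | 15 Jun 2018, TEAE |
| --/AUG/2018 | ongoing | 15 Jun 2018, TEAE | 1 Aug 2018, TEAE |
| --/NOV/2018 | ongoing | 15 Jun 2018, TEAE | 1 Nov 2018, not TEAE |
| --/---/2018 | ongoing | 15 Jun 2018, TEAE | 15 Jun 2018, TEAE |
| --/DEC/2017 | ongoing | 1 Dec 2017, not TEAE | 1 Dec 2017, not TEAE |
| --/JAN/2019 | none | 1 Jan 2019, not TEAE | 1 Jan 2019, not TEAE |

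**Results.**

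1. For an unresolved event with only the day missing, the literal reading resets 12 of the 12 months of the start year to first dose. The respective reading resets 1 of 12.
2. TEAE status differs in the first, second and sixth rows. A March onset is at least 76 days before first dose (31 Mar to 15 Jun: 30 + 31 + 15). A November onset is at least 32 days after the on-treatment period ends (30 Sep to 1 Nov: 31 + 1). In both cases the recorded month alone rules out treatment emergence.
3. The minimum with the resolution date protects the third row. It cannot protect the November row, because such an event resolves after treatment start.
4. The August row changes in date but not in status.
5. When the month is missing, when it equals the start month, or when the year differs, the two readings agree.

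**The case against.** The best defence is that the literal reading is the less natural one. A match on month and year always implies a match on year, so on that reading the month-and-year condition does nothing. A reader who wants each condition to do some work will compare month and year when both are recorded, and year when only the year is. The Part C plan says exactly this. The argument stands as evidence of intent. It does not settle the specification: the Part C plan is a separate document dated 2021 that covers Part C only, and the Parts A/A2/B1 sentence does not state the restriction.

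There are also mitigations. Imputed values are flagged in listings, all adverse events are listed with their collected fields whether treatment-emergent or not, and a data review meeting precedes each database lock. For TEAE status the literal reading can only over-count. The reporting windows that decide whether such early or late events are collected at all may stand in the protocol. These points limit the harm, but they do not tell the programmer which rule to code.

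Three stronger inferences are tempting, and the document does not support them:

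- *Every pre-treatment event with a partial date becomes treatment-emergent.* It does not. The replacement is the earlier of treatment start and resolution, so an event resolved before first dose stays pre-treatment.
- *Late events moved to Day 1 enter the dose-limiting toxicity window and affect the maximum tolerated dose.* Section 15.1 takes dose-limiting toxicities from an eCRF flag, and an imputed date cannot create that flag.
- *Moving an on-treatment event to Day 1 distorts the tables.* Sections 15.2.1 and 15.2.2 plan no summary by cycle or by time to onset, so those frequency tables do not change.

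**Conclusion.** The point holds as a defect of wording with a real but bounded consequence. Read literally, Section 15.2 misclassifies two kinds of event with a day-missing onset in the treatment-start year: those from a known month before the start month that are unresolved or resolve on or after first dose, and those from a known month lying wholly after last dose + 30 days. Both are wrongly counted as TEAEs. Read in the respective sense, the rule is sound. It should not be described as a deliberate choice of a poor method.

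The number of such events cannot be determined from the document and may be small. As an illustration only, in a dose group of six, the denominator in the Section 15.1 definition of the maximum tolerated dose, one subject wrongly counted shifts an incidence by 1/6, about 17 percentage points. The example dates are assumed. The pre-treatment result needs only that the recorded month precedes the start month within the same year, and the late result that the recorded month lies beyond the on-treatment period within that year.

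**What to change.** Replace the first onset bullet and its fallback in Section 15.2 with wording such as:

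> If the onset date is completely missing; or only the day is missing and month and year equal those of treatment start; or day and month are both missing and the year equals that of treatment start: use the minimum of treatment start and AE resolution date. In all other cases a missing day or month is set to 1.

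This keeps the existing protection by the resolution date and adopts the split used for Part C. It costs one sentence and no new data. If the onset derivation has already been programmed, check which reading was coded and whether any day-missing onset in the treatment-start year, outside the start month, changes TEAE status.

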8.2 Definition of Analysis Sets and Subgroups

Screening Analysis Set (SCR)

The screening analysis set includes all subjects who signed the informed consent form.

Safety Analysis Set (SAF)

The SAF will include all enrolled subjects who received at least 1 dose of study drug (either M4344 or carboplatin (Part B1 only)) with the actual amount > 0 mg. Analyses performed on the SAF will consider subjects' planned dose group.

Dose Limiting Toxicity (DLT) Evaluable Set

The DLT evaluable set includes all enrolled subjects who received at least one dose of M4344 and either:

- Experienced a DLT before the end of Cycle 1 (21 days after start of treatment) or
- Received the following minimum required doses of study drug(s) in Cycle 1 (21 days from start
 of treatment):
 - Part A: at least 80% (5 out of 6) of scheduled M4344 doses through the end of Cycle 1
 - Part B1: carboplatin dose on Day 1 and M4344 dose on Days 2 and 9
 - Part A2: at least 80% (34 out of 42 for BID regimen or 17 out of 21 for QD regimen) of scheduled M4344 doses through the end of Cycle 1.

Subjects who are withdrawn before they meet one of these criteria will be excluded from the determination of the MTD (and will be replaced), and thus will be excluded from the DLT evaluable set.

Full Analysis Set (FAS)

The FAS is defined as all enrolled subjects who satisfy all of the following criteria:

- received at least 1 dose of study drug with the actual amount > 0 mg
- have a baseline scan with a measurable target lesion (sum of diameters of all target lesions > 0 mm)
- have at least 1 disease assessment on treatment with a measureable target lesion (sum of diameters of all target lesions >= 0 mm); or subjects who have discontinued the study due to either progressive disease or death.

Modified Full Analysis Set (mFAS)

The mFAS is defined as all enrolled subjects who satisfy all of the following criteria:

- received at least 1 dose of study drug with the actual amount > 0 mg
- have a baseline scan with a measurable target lesion (sum of diameters of all target lesions >= 0 mm)

Pharmacokinetic Analysis Set (PAS)

The PAS will include all enrolled subjects who receive at least one dose of M4344 with the actual amount > 0 mg and provide at least one measurable post-dose concentration. Subjects will be analyzed according to the actual treatment they received. All PK analyses will be based on this analysis set.

Table 1 Summary of Analysis and Associated Analysis Set

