12.3 Concurrent Procedures

All concurrent procedures, which were undertaken any time during the trial, will be summarized according to the eCRF page "Non-Pharmacological Treatment or Procedures" (Parts A and B1) or "Concomitant Procedures" (Part A2).

Concurrent procedures will be derived in the same way as concomitant medications. In case the date values will not allow unequivocal allocation of a procedure as a concurrent procedure, the procedure will be considered a concurrent procedure.

All concurrent procedure data will be listed, including flags for procedures that took place prior to, on or after the date of first dose of a trial drug (M4344 or carboplatin, as applicable), or within 30 days after the last dose of a trial drug (M4344 or carboplatin, whichever was taken last).

13 Treatment Compliance and Exposure

Analysis set: SAF

Dosing information is collected from the "Study Drug Administration: VX-803 – Clinic Dose" (Parts A and B1), "Study Drug Administration Home Dose: VX-803" (Parts A and B1), "Study Drug Administration: Carboplatin" (part B1 only), "End of Dosing" (Parts A and B1), "M4344 Time of Administration" (Parts A2), and "M4344 Administration Details" (Part A2) eCRF pages.

- Part A: M4344 is taken twice a week (on treatment days 1, 4, 8, 11, 15, and 18) of a 21-day treatment cycle.
- Part A2: M4344 is taken twice a day every day of a 21-day treatment cycle. Once daily dosing and additional cohorts with a planned drug holiday may also be explored.
- Part B1:
 - Carboplatin is administered by infusion on treatment day 1 of a 21-day treatment cycle
 - M4344 is taken on treatment days 2 and 9 of a 21-day treatment cycle. An additional cohort with one additional dose on day 5 may be explored.

Total number of administrations of M4344

Total number of administrations is calculated as the sum of administrations that a subject received across cycles where actual dose received is > 0 mg or the eCRF field for "Did the subject take the dose of VX-803?" on the "Study Drug Administration Home Dose: VX-803" is marked as "Yes" or if the eCRF field for "Was VX-803 administered?" on the "Study Drug Administration: VX-803 – Clinic Dose" is marked as "Yes."

Total number of infusions of carboplatin (part B1 only)

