15.2.1 All Adverse Events

AEs will be summarized by worst severity (according to the National Cancer Institute – Common Terminology Criteria for Adverse Events (NCI-CTCAE) version 4.0) per subject, using MedDRA preferred term as event category and MedDRA primary system organ class (SOC) body term as Body System category.

If an AE is reported for a given subject more than once during treatment, the worst severity and the worst relationship to trial treatment will be tabulated. In case a subject had events with missing and non-missing grades, the maximum of the non-missing grades will be displayed.

The following overall frequency tables will be prepared by dose group and overall. In addition the tables will be provided by PT and primary SOC in alphabetical order:

- Any TEAE
- Any trial drug related TEAEs*
- Any serious TEAEs
- Any non-serious TEAEs
- Any trial treatment related serious TEAEs*
- Any TEAE by NCI-CTCAE severity grade (≥3, ≥4)
- Any trial drug related TEAE by NCI-CTCAE severity grade (≥3, ≥4)*
- Any TEAEs leading to death (TEAEs with Grade 5 or outcome "fatal" if grade 5 not applicable)
- Any trial drug related TEAEs leading to death (TEAEs with Grade 5 or outcome "fatal" if grade 5 not applicable)*

Tables annotated by * will be summarized as follows:

- Parts A and A2 with a summary for M4344
- Part B1: summaries for M4344, carboplatin, and M4344/carboplatin

The listing for all AEs (whether treatment-emergent or not) will include all the data fields as collected on the "Adverse Events" eCRF page.

Clinical trial.gov and EudraCT -requirements

Summary tables for non- serious adverse events excluding SAEs applying frequency threshold of 5% will be provided by study part. The non-serious AEs are not restricted to non-serious TEAEs.

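### In Part B1, a blank relationship to M4344 counts as M4344-related even when the event began before any M4344 dose or the participant never received M4344 (minor)

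*SAP*

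**What the plan says.** All references are to the SAP for Parts A, A2 and B1 unless Part C is named.

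- **Relatedness (Section 15.2).** Related events are "adverse events with relationship to study treatment reported by the investigator and those of unknown relationship (i.e. missing data for relationship"). The M4344 line names Part B1 explicitly: "Relationship to VX-803' (Parts A and B1) or 'Relationship with M4344' (Part A2) = 'Related', 'Possibly Related', or missing". A parallel line covers carboplatin. Neither line has a condition on onset date or exposure.
- **Treatment emergence (Sections 15.2 and 9).** TEAEs are "those events with onset dates occurring within the on-treatment period as defined in Section 9". Section 9 states: "The on-treatment period is defined as the date of the first dose of a trial drug (M4344 or carboplatin as applicable"), running to 30 days after the last dose or to death, whichever is earlier.
- **Safety set (Section 8.2).** "The SAF will include all enrolled subjects who received at least 1 dose of study drug (either M4344 or carboplatin (Part B1 only")). Participants are analysed in their planned dose group.
- **Schedule in Part B1 (Section 13).** The infusion comes first: "Carboplatin is administered by infusion on treatment day 1 of a 21-day treatment cycle". The investigational drug follows one day later, under a separate bullet: "M4344 is taken on treatment days 2 and 9 of a 21-day treatment cycle".
- **Output (Section 15.2.1).** The starred tables of related TEAEs (any, serious, Grade 3 or higher, Grade 4 or higher, fatal) are split by drug: "Part B1: summaries for M4344, carboplatin, and M4344/carboplatin". If a participant reports an event more than once, the worst relationship is tabulated.

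**The concern.** Counting a missing relationship as related is a sensible safeguard when the drug could have contributed. In Part B1 the safeguard reaches further than that. Treatment emergence starts with carboplatin, so some TEAEs begin when the participant has had no M4344. For those events a blank M4344 field is turned into a positive attribution to a drug not yet given, or never given.

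Adverse events are part of the primary safety objective in Part B1, and the drug-specific tables exist to separate M4344 from carboplatin. For the M4344 tables this gap can only add events to the M4344-related counts. Dose groups in an escalation study may be small, so a single participant can be visible in a percentage.

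**Working it through.** The plan gives no figure on this point to reproduce. The check applies its definitions in order and then bounds the size.

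**Case 1: an event starting on Cycle 1 Day 1, after the infusion, with the M4344 relationship blank**

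1. The first dose of a trial drug is carboplatin on Day 1, so the on-treatment period is open (Section 9).
2. Onset lies in that period, so the event is a TEAE (Section 15.2). It is not a pretreatment event, because that category ends at the start of M4344 or carboplatin, as applicable.
3. The participant is in the safety set through carboplatin alone, in the planned M4344 dose group (Section 8.2).
4. The M4344 relationship is missing, so the event is M4344-related (Section 15.2).
5. It enters the M4344 column of the starred tables (Section 15.2.1). Since the worst relationship is taken, one blank record can be enough for that term.
6. The first M4344 dose is on Day 2 (Section 13), after onset.

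**Case 2: a participant who receives carboplatin and never M4344.** Steps 1 to 5 apply to every TEAE with a blank M4344 field. There is no M4344 exposure at any time.

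No other section removes either kind of event.

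**Length of the window**

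- On schedule: from Day 1 to the Day 2 dose, 1 day of the 21-day cycle, 1/21 = 4.8%. It is longer if the first M4344 dose is late.
- One infusion and no M4344: the infusion day plus 30 days = 31 on-treatment days, unless death comes first.

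**Effect on a table row.** The tables count participants. If k of n participants are already M4344-related in a row, an affected participant changes the row only if not already among those k:

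(k + 1)/n − k/n = 1/n

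| Assumed group size n | Maximum change per affected participant |
|---|---|
| 6 | 1/6 = 16.7 points |
| 3 | 1/3 = 33.3 points |

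If the participant already has another M4344-related event in that row, or the site entered an explicit unrelated assessment, the change is 0. The document gives neither adverse event counts nor a rate of blank fields, so no expected value can be computed.

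**The case against.** The strongest reply is that missing-as-related is a deliberate conservative convention. The Part C plan uses it too (its Section 15.1). It may overstate M4344 toxicity but does not hide it. Section 15.2 treats a blank as missing data, not as a code for a drug not yet dosed, and nothing shows that sites leave the field blank before M4344. A data review meeting precedes each database lock (Section 6.1), and the listing of all adverse events carries every collected field (Section 15.2.1), so blanks can be found. All of this stands, and it makes the point minor. It does not answer the logic: before first exposure a relationship at onset is not possible, so there is nothing for the convention to be conservative about.

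A second reply concerns the remedy. A rule that classed every event with onset before M4344 as unrelated would override explicit investigator entries. It would also catch events that began on Day 1 and worsened after M4344. Section 15.2 imputes some incomplete onset dates to the start of trial treatment, which in Part B1 is the carboplatin day, so such a rule would also reclassify events that may really have followed M4344. That objection is right, and the change has to be narrower.

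A reader might also infer that the gap distorts the MTD or the tables of events leading to discontinuation. The document does not support either. DLTs come from their own eCRF field (Section 15.1), and the DLT evaluable set requires at least one M4344 dose. The discontinuation rows in Section 15.2.2 are split by the drug that was stopped, and carry no stated split by the drug to which the event is related.

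**Conclusion.** The gap is real, narrow and minor. As written, Section 15.2 gives an attribution that is impossible in time at onset for Part B1 events with a blank M4344 relationship that start before the first M4344 dose, or that occur in participants who never received M4344. The affected outputs are the M4344-specific related tables in Section 15.2.1: any, serious, Grade 3 or higher, Grade 4 or higher, and fatal.

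The figure of 16.7 points per affected participant is a maximum. It rests on an assumed group of 6 and on that participant having no other M4344-related event in the row. The effect is zero if sites always record an explicit relationship.

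It is tempting to conclude that carboplatin-only toxicity is being reported as M4344 toxicity. The document does not support that. A blank field does not show that carboplatin caused the event, and how often blanks occur is not shown. What can be said is that, at onset, the event could not be attributed to M4344.

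**What to change.** Add to Section 15.2:

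> In Part B1, a missing relationship to M4344 is not counted as M4344-related if the participant never received M4344, or if the AE has a complete (non-imputed) onset date strictly before the date of the first M4344 dose and no recorded worsening on or after that date. Explicit investigator entries are kept as reported. Missing counts as related for all other events, including same-day and imputed onsets.

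The carboplatin rule needs no change: an event removed from the M4344 tables stays in the carboplatin tables if that field is blank, Related or Possibly Related.

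The cost is a short addition to the text and one exposure and date check in programming. M4344-related counts in Part B1 may fall slightly. Events with same-day or imputed onset that in fact preceded M4344 will still count as related, which is the price of keeping the rule conservative where timing is uncertain.
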